6.3. Exploratory Efficacy Endpoints

6.3.1. Definition of Exploratory Efficacy Endpoints

PPD

[Redacted text block]

6.3.2. Analysis Methods for Exploratory Efficacy Endpoints

PPD

[Redacted text block]

PPD

6.4. Changes From Protocol-Specified Efficacy Analyses

There are no changes from protocol-specified efficacy analyses.

7. SAFETY ANALYSES

Safety data will be summarized for subjects included in the safety analysis set. Summaries of safety data (treatment-emergent [TE] adverse events [AEs], TE maximum toxicity grades, changes from baseline in laboratory and vital signs parameters) will include all data collected on or after the first dose date of any study drug through the last dose date of any study drug plus 30 days for subjects who have stopped all study drugs, and all available data in the database for subjects still on treatment at the time of the analysis.

All safety data (except for laboratory tests with results that were cancelled by the lab) will be included in data listings based on the safety analysis set.

7.1. Adverse Events

7.1.1. Adverse Event Dictionary

Clinical and laboratory AEs will be coded using the current version of Medical Dictionary for Regulatory Activities (MedDRA). System organ class (SOC), high level group term (HLGT), high level term (HLT), preferred term (PT), and lower level term (LLT) will be attached to the clinical database.

7.1.2. Adverse Event Severity

Adverse events are graded by the investigator according to the Gilead Sciences, Inc. (Gilead) Grading Scale for Severity of Adverse Events and Laboratory Abnormalities as specified in the clinical study protocol. The severity grade of events for which the investigator did not record severity will be categorized as “missing” for tabular summaries and data listings, and will be considered the least severe for the purposes of sorting for data presentation.

7.1.3. Relationship of Adverse Events to Study Drug

The relationship of AE to study drug will be assessed by investigators as “Yes” or “No”. Events for which the investigator did not record the relationship to study drug will be considered to be related to study drug for summary purposes. However, data listings will present the relationship as missing.

7.1.4. Serious Adverse Events

Serious adverse events will be identified and captured as SAEs if AEs met the definitions of SAE specified in the study protocol. Serious adverse events captured and stored in the clinical database will be reconciled with the SAE database from the Gilead Drug Safety and Public Health Department before database finalization.

7.1.5. Treatment-Emergent Adverse Events

7.1.5.1. Definition of Treatment-Emergent

Treatment-emergent AEs are

- Any AEs with onset date of on or after the study drug start date and no later than 30 days after permanent discontinuation of study drug or
- Any AEs leading to premature discontinuation of study drug

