6.1. Subject Enrollment and Treatment Assignment

6.2. Pretreatment Assessments

6.2.1. Screening Visit (Day -28 to Day -1)

Screening assessments will be completed within 28 days of the Baseline/Day 1 visit. The screening window can be extended to 42 days for subjects requiring liver biopsy or additional HCV genotype testing.

Subjects will be screened to determine eligibility for participation in the study. The following will be performed and documented at screening:

- Obtain signed informed consent
 - A separate informed consent will be required from subjects participating in the intensive pharmacokinetic and/or pharmacogenomic sub-studies.
- Determine inclusion eligibility (Reference Section [4.2](#) and [4.3](#))
 - If the presence of cirrhosis is determined, then appropriate diagnostic imaging (e.g., CT or Ultrasound) should be performed to exclude the presence of hepatocellular carcinoma (HCC)

- Obtain medical history (Reference Section 6.6.2)
- Perform complete physical examination
- Obtain body height and weight
- Obtain vital signs (resting blood pressure, pulse, respiratory rate and temperature)
- Perform 12-lead ECG
- Assessment of AEs and concomitant medications
- Obtain blood samples for tests
 - Hematology & Chemistry
 - Coagulation tests
 - HCV RNA
 - Serum β -hCG pregnancy test for females of childbearing potential only
 - IL28B genotype
 - Determination of genotype and subtype of HCV infection
 - HCV antibody, HIV 1/2 antibody, and HBV surface antigen (HBsAg)
 - HbA1c
 - TSH
- Obtain urine sample for:
 - Urinalysis

Record any adverse events occurring after signing of the consent form.

Subjects meeting all of the inclusion criteria and none of the exclusion criteria will return to the clinic within 28-42 days after screening for entry into the study.

From the time of obtaining informed consent through the first administration of investigational medicinal product, record all serious adverse events (SAEs), as well as any non-serious adverse events related to protocol-mandated procedures on the adverse events case report form

(CRF/eCRF). All other untoward medical occurrences observed during the screening period, including exacerbation or changes in medical history are to be captured on the medical history CRF/eCRF. See Section 7 Adverse Events and Toxicity Management for additional details.

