8.6.2. Adverse Events

Clinical and laboratory adverse events will be coded using the Medical Dictionary for Regulatory Activities (MedDRA). System Organ Class (SOC), High-Level Group Term (HLGT), High-Level Term (HLT), Preferred Term (PT), and Lower-Level Term (LLT) will be attached to the clinical database.

Events will be summarized on the basis of the date of onset for the event. A treatment-emergent adverse event will be defined as any new or worsening adverse event that begins on or after the date of first dose of IMP up to the date of last dose of IMP plus 30 days.

Summaries (number and percentage of subjects) of treatment-emergent adverse events (by SOC, HLT, and PT) will be provided:

- All AEs,
- All study drug-related AEs,
- Combined Grade 2, 3 and 4 AEs,
- Combined Grade 3 and 4 AEs,
- Combined Grade 2, 3 and 4 study drug-related AEs,
- Combined Grade 3 and 4 study drug-related AEs,
- All AEs that caused permanent discontinuation from study drug,
- All AEs that caused change in dose or temporary interruption of study drug,

- All SAEs (including death), and
- All study drug-related SAEs

All AEs collected during the course of the study will be presented in data listings.

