7.1.6. Summaries of Adverse Events and Deaths

A brief summary of AEs will show, for China and Overall (i.e., China plus Korea plus Taiwan), the number and percentage of subjects who (1) had any TE AE, (2) had any Grade 3 and 4 TE AE, (3) had any Grade 2, 3 and 4 TE AE, (4) had any TE treatment-related AE, (5) had any Grade 3 and 4 TE treatment-related AE, (6) had any Grade 2, 3 and 4 TE treatment-related AE, (7) had any TE SAE, (8) had any TE treatment-related SAE, (9) AEs leading to permanent discontinuation from LDV/SOF (10) had any AE leading to interruption of LDV/SOF and (11) TE death during the study.

Summaries (number and percentage of subjects) of adverse events (by SOC and PT) will be provided for China and Overall using the safety analysis set as follows:

- All TE AEs
- Combined Grade 3 or 4 TE AEs
- Combined Grade 2, 3 or 4 TE AEs
- TE treatment-related AEs
- Combined Grade 3 or 4 TE treatment-related AEs
- Combined Grade 2, 3 or 4 TE treatment-related AEs

- TE SAEs
- TE treatment-related SAEs
- Adverse Events Leading to permanent discontinuation from LDV/SOF
- All deaths

Multiple events will be counted once only per subject in each summary. For data presentation, SOC will be ordered alphabetically, with PT sorted by decreasing total frequency within an SOC. For summaries by severity grade, the most severe event will be selected.

In addition to the presentation by SOC and PT, summaries will also be presented by PT only, ordered by decreasing total frequency for: (1) TE treatment-related AEs; (2) TE AEs that occurred in more than 5% of subjects within any region; (3) AEs leading to permanent discontinuation of LDV/SOF; (4) TE SAEs; and (5) TE grade 3 or 4 AEs.

Data listings, with a variable indicating whether the event is treatment-emergent, will be provided for the following:

- All AEs
- SAEs
- Deaths
- AEs leading to permanent discontinuation from LDV/SOF
- Grade 3 and 4 AEs

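### SAP 7.1.5.1 leaves worsening events out of its treatment-emergent definition, and SAP 7.1.6 cuts the protocol's interruption-AE summary to one subject count; neither departure is declared

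*SAP*

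**What the plan says.** Protocol 8.6.2 sets the rule for AEs: "A treatment-emergent adverse event will be defined as any new or worsening adverse event that begins on or after the date of first dose", up to 30 days after the last dose. It then lists treatment-emergent summaries by SOC, high-level term (HLT) and PT. One of them is "All AEs that caused change in dose or temporary interruption of study drug".

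SAP 7.1.5.1 has two limbs. The first is "Any AEs with onset date of on or after the study drug start date and no later than 30 days after permanent discontinuation". The second is "Any AEs leading to premature discontinuation of study drug", with no condition on onset date. Neither limb mentions worsening, and SAP 7.1.5.2 resolves incomplete dates from the onset date alone.

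SAP 7.1.6 keeps interruptions as item (10) of the brief AE summary, subjects who "had any AE leading to interruption of LDV/SOF", which Appendix 1 places in Table 15. Neither 7.1.6 nor Appendix 1 contains a breakdown of these events by SOC and PT.

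Events with onset before dosing can be on the AE form. From consent to first dose, Protocol 6.2.1 tells sites to "record all serious adverse events (SAEs), as well as any non-serious adverse events related to protocol-mandated procedures on the adverse events case report form". All other screening events go to medical history.

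**The concern.** Safety and tolerability are a primary objective and there is no control arm, so the AE tables are the main safety result. The protocol's definition has a worsening limb and the SAP's does not. An event already on the AE form at Day 1 that becomes more severe on LDV/SOF could be treatment-emergent under the protocol and not under the SAP.

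The SAP is also uneven within itself. For laboratory data, 7.2.2.1 counts any rise of at least one grade from baseline as treatment-emergent. For clinical AEs it has no such rule and gives no reason for the difference.

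On interruptions, a reader of the tables would learn how many subjects interrupted treatment because of an AE, but not for which events. Protocol 7.6 allows no dose reduction, so interruption is the only dose modification short of stopping that can be tabulated.

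Neither departure is flagged. SAP 4.4 does explain a slight change to the PK analysis set, so a reader could expect these changes to be explained too.

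**Working it through.** The first part is a comparison of text; the plan gives no figure to reproduce. Take an AE on the form with onset before first dose that rises in grade on drug. Under Protocol 8.6.2, read as a worsening that begins on drug, it is treatment-emergent in every case below. Under the SAP:

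| How it is recorded and what follows | Treatment-emergent under SAP 7.1.5.1? | Where it appears |
|---|---|---|
| New record dated from the worsening | Yes, first limb | All relevant tables; no difference from the protocol |
| Original record, leads to discontinuation | Yes, second limb | Treatment-emergent tables and discontinuation Tables 22 and 28 |
| Original record, leads to interruption only | No | Brief-summary item (10) in Table 15, which is not limited to treatment-emergent events; listings |
| Original record, fatal, drug not discontinued for it | No | All Deaths (Table 25); listings |
| Original record, none of these | No | Listings only |

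The gap is therefore the last three rows, and for the treatment-emergent tables only. It can arise only for a screening SAE or procedure-related AE. Other pre-existing conditions are not on the AE form. If one worsens after dosing it becomes an AE under Protocol 7.1.1, with no earlier AE record to carry an old onset date.

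*Size.* The documents give no frequency. Assume 0 to 3 affected subjects among about 200 in China:

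- Upper end for a table in which none of the three is otherwise counted, for example treatment-emergent SAEs: 3 / 200 = 1.5 percentage points.
- For the any-AE row, a subject counts once however many events occur (SAP 7.1.6). Protocol 1.2.2.3 reports AEs in 64% of Japanese subjects on SOF/LDV. If that rate applied to these subjects, 3 × (1 − 0.64) = 1.08 would be newly counted, and 1.08 / 200 = 0.54 points.
- Lower end: 0, if no such event occurs or if each worsening is a new record.

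*Interruptions.* Set side by side, the protocol asks for a breakdown by SOC, HLT and PT, and the SAP supplies one row of Table 15. The SAP omits the HLT level from all its AE summaries, so the loss specific to interruptions is the whole SOC/PT table. The individual events remain in Listing 10, which covers all AEs.

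**The case against.** The strongest reply is that the two definitions may not differ in practice. The protocol's own wording turns on when an event begins, and it adds: "Events will be summarized on the basis of the date of onset for the event". Protocol 7.1.1 makes a pre-existing event that increases in severity an AE in its own right. If that AE gets its own onset date, the SAP's first limb captures it. This stands in large part: neither document states the recording convention, and the gap needs the unfavourable one. It does not remove the point, because the protocol's mention of worsening adds nothing if only newly dated records count.

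The exposed group is also close to empty. A subject with an unresolved screening SAE must still be in generally good health and free of an illness that may interfere with the study. Worsening laboratory values are caught by SAP 7.2.2.1. Both observations are fair and keep the point minor.

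Several stronger readings are tempting, and the documents do not support them:

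- A reader might infer that the SAP goes by onset date alone, or that a worsened screening event reaches no AE table. The second limb has no onset condition, and item (10) and All Deaths are not restricted to treatment-emergent events.
- A reader might infer that the interruption summary is gone. The subject count is kept.
- A reader might infer that the SAP rule can only lower counts. The second limb brings in discontinuation AEs whatever their onset, which Protocol 8.6.2 does not, so it can also raise them.
- A reader might take the SAP as asserting that its safety analyses match the protocol. The no-change statement in 6.4 covers efficacy only; on safety the SAP is silent.

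**Conclusion.** The point holds as two undeclared departures from Protocol 8.6.2, both minor.

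First, the SAP omits worsening from the treatment-emergent definition. This has an effect only if a screening SAE or procedure-related AE is ongoing at Day 1, rises in grade on drug, stays under its original record and does not lead to discontinuation. On the assumed 0 to 3 subjects in about 200, the effect is 0 to 1.5 points on a given count. Both the number of subjects and the recording convention are assumptions.

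Second, one protocol-specified table is reduced to a subject count. This does not depend on any recording convention. The table may be short, since Protocol 7.6 does not permit restarting after a stop for toxicity.

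The primary safety endpoint, AEs leading to permanent discontinuation, is unaffected: the second limb and the discontinuation tables cover those events whatever their onset date.

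**What to change.** In SAP 7.1.5.1, add a limb counting any AE with pre-dose onset whose severity grade rises between first dose and 30 days after study drug is permanently stopped, dated from the rise. If the database does not hold the date of a grade change, state instead that a worsening is entered as a new AE record dated from the worsening; the first limb then does the work.

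In SAP 7.1.6 and Appendix 1, add an SOC/PT table of AEs leading to interruption of LDV/SOF. No separate listing is needed, because all AEs are already listed.

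The cost is a few lines of text, one programming condition and one table. The downside is that AE counts may be slightly higher.

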7.1.5.2. Incomplete Dates

If the date of onset is incomplete, then the month and year (or year alone if month is not recorded) of onset determine whether the AE is treatment emergent. The event is treatment emergent if the month and year of onset (or year of onset) of the event meets both of the following criteria:

- The same as or after the month and year (or year) of the first dose of any study drug
- The same as or before the month and year (or year) of the 30th day after the date of the last dose of any study drug

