7.4. Concomitant Medications

Concomitant medications (ie, medications other than study drug that are taken while receiving study drug) will be coded using the World Health Organization (WHO) Drug Dictionary. The WHO preferred name and drug code will be attached to the clinical database. Use of concomitant medications up to the last dose of any study drug will be summarized (number and percentage of subjects) for China and Overall, WHO drug class, and WHO generic name. Multiple drug use (by preferred name) will be counted once only per subject. The summary will be sorted alphabetically by drug class and then by decreasing total frequency within a class.

For purposes of programming, any medication with a stop date that is on/prior to first dosing date or start date that is after the last dose of any study drug will be excluded from this summary. Otherwise, dates that are completely missing will be included in the summary. If a partial stop date is entered, then the month and year (if day is missing) or year (if day and month are

missing) that is prior to the study drug start date will be excluded from the summary. If a partial start date is entered, then the month and year (if day is missing) or year (if day and month are missing) that is after the study drug stop date will be excluded from the summary.

Summaries of concomitant medications will be provided for the safety analysis set. No inferential statistics will be generated.

A listing of all concomitant medications reported during the study will be provided.

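### SAP 7.1.5.2 can count an adverse event that ended before first dose as treatment-emergent, because an incomplete onset date is judged without the stop date

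*SAP*

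**What the plan says.** SAP 7.1.5.1 defines treatment-emergence by onset: "Any AEs with onset date of on or after the study drug start date and no later than 30 days after permanent discontinuation of study" … A second limb adds any event that leads to early stopping of the drug. Protocol 8.6.2 sets the same lower bound, with an upper bound that also adds 30 days: "any new or worsening adverse event that begins on or after the date of first dose of IMP up to the date of last dose" …

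For incomplete onset dates, SAP 7.1.5.2 states that "then the month and year (or year alone if month is not recorded) of onset determine whether the AE is treatment emergent". It then gives two criteria and classes an event that meets both as treatment-emergent:

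- lower bound: "The same as or after the month and year (or year) of the first dose of any study drug";
- upper bound: "The same as or before the month and year (or year) of the 30th day after the date of the last dose of any study" …

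Neither criterion mentions the stop date, and no other part of the SAP brings it in for adverse events.

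Pre-dose events can be in the data. From consent to first dose, Protocol 6.2.1 tells sites to "record all serious adverse events (SAEs), as well as any non-serious adverse events related to protocol-mandated procedures on the adverse events case report form". Protocol 9.1.5 makes both start and end dates of adverse events required source data.

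**The concern.** An event that ended before first dose cannot have begun on or after it. If its onset date is partial and its stop date is recorded, the trial's own data settle the question, yet the rule gives the opposite answer. This is a stated rule that misclassifies, not a detail left open.

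What is at stake is the incidence of treatment-emergent events, including serious ones, in a study with no control arm against which to read a stray count. SAP 7.1.3 could compound it: an event with no recorded relationship is summarised as drug-related, so a resolved pre-dose serious event with a partial onset and blank causality would also enter the treatment-related table.

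**Working it through.** The plan states no figure for this rule, so the check is one of logic, followed by the size of one misclassification.

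**1. Test dates.** First dose is taken as 20 March and treatment as 84 days (SAP 4.3.2.1), so the last dose is 11 June and the 30th day after it is 11 July. The upper bound is then July of that year.

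| Recorded onset | Recorded stop | SAP 7.1.5.2 as written | SAP 7.1.5.1, given the stop date | With a stop-date condition |
|---|---|---|---|---|
| March, day unknown | 8 March | treatment-emergent | not | not |
| February, day unknown | 8 March | not | not | not |
| Year only, dosing year | 8 March | treatment-emergent | not | not |
| March, day unknown | missing | treatment-emergent | cannot be decided | treatment-emergent |

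Rows 1 and 3 are the defect. Row 2 shows its limit: a partial onset in an earlier month is already excluded. Row 4 shows that the cautious default survives the repair.

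**2. How often a partial date would meet the rule.** Protocol 6.2.1 gives a 28-day screening window, extendable to 42. Assume that onset is uniform over the window, and take every first-dose date in a four-year calendar cycle. The share of pre-dose days that fall in the same period as first dose is:

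| Window | Same month | Same year |
|---|---|---|
| 28 days | 52% | 96% |
| 42 days | 35% | 94% |

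The same-year figures can be checked by hand: 1 − [(28 + 1)/2]/365.25 = 0.960 and 1 − [(42 + 1)/2]/365.25 = 0.941. These are shares of screening events that already have an incomplete onset date. The documents give no count of such events.

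**3. Size of one misclassification.** The denominators are the planned 200 subjects in China and 360 Overall (Protocol 3.2).

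- China: 1/200 = 0.50 percentage points.
- Overall: 1/360 = 0.28 percentage points.

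These are maxima, because SAP 7.1.6 counts a subject once per summary. As an illustration, assume that the 64% adverse event incidence reported with SOF/LDV alone in the Japanese study (Protocol 1.2.2.3) applied here, independently of any pre-dose event. The expected addition to the row for any treatment-emergent event would be (1 − 0.64) × 0.50 = 0.18 points in China and (1 − 0.64) × 0.28 = 0.10 points Overall. The full 0.50 and 0.28 points apply only in rows where the subject has no other event, such as serious events.

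**The case against.** The strongest reply is that the trigger is narrow. Four things must coincide: a pre-dose event on the adverse event form, an incomplete onset date, a partial onset that matches first dose, and a recorded stop date before first dose. Screening is short, start and end dates are required, discrepancies are queried (Protocol 9.1.6), and data are finalised after queries are resolved (SAP 2.3). A year-only onset for an event that arose after consent would be unusual. All of this stands, and nothing in the documents shows that such an event exists.

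A reader might infer a wider problem in three ways that the documents do not support.

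- *Every screening event is exposed.* Protocol 6.2.1 does have a line on recording any event after consent. It then sends only serious and procedure-related events to the adverse event form before dosing, and the rest to medical history. Protocol 7.3 agrees.
- *The serious event tables are the most exposed.* Each extra count would show more in those tables, but SAP 7.1.4 reconciles serious events with the safety department's database before finalisation. That is an added check which may complete some dates.
- *SAP 7.4 proves an oversight.* That section does exclude "any medication with a stop date that is on/prior to first dosing date". But a concomitant medication is defined by use during treatment, whereas treatment-emergence is defined by onset. The comparison shows that the SAP can program with stop dates, and no more.

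Two other replies fail. One is that the rule is deliberately cautious: caution is sound when timing is unknown, but a stop date before first dose removes the doubt. The other is that SAP 7 limits safety summaries to data from first dose onward: that general sentence gives no method for partial dates, and 7.1.5.2 is the specific rule to be programmed.

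**Conclusion.** The point holds as a minor error of classification. On its stated wording, SAP 7.1.5.2 can label as treatment-emergent an event that the recorded stop date shows to have ended before first dose, contrary to SAP 7.1.5.1 and Protocol 8.6.2.

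The error runs only upward. Its ceiling is 0.5 points per affected subject in China and 0.28 points Overall at the planned sample sizes. The number of affected subjects cannot be derived from the documents and may well be zero.

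It would be wrong to read this as a threat to the main results. SVR12 does not use adverse event dates. The primary safety endpoint is an adverse event that makes the subject stop the drug for good (Protocol 8.1.2), and an event that resolved before the first tablet should not be one. The change is worth making because it is nearly free.

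**What to change.** Add to SAP 7.1.5.2, in words such as: *an adverse event with an incomplete onset date is not treatment-emergent if its stop date is before the date of first dose or, where the stop date is itself partial, if the recorded month and year (or year) is before that of first dose. If the stop date is missing or does not settle the order, the event remains treatment-emergent.* The second limb of 7.1.5.1, on events that lead to early stopping, stays as it is.

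The clause on partial stop dates matters mainly for year-only onsets. If the onset month is known and equals that of first dose, a stop month before it would be a data error to query.

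The cost is one sentence and one programming condition, with no new data and no imputation, so it fits SAP 3.6.1. There is one small downside. Korea and Taiwan were already reported under the SAP of 22 July 2014 (SAP 1), whose rule is not available here. Apply the revised rule to their data in the Overall tables, and note in the study report any adverse event flag that differs from the interim report.
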